#### Hypothesis:

$H_0: \mu_{iNO\ 75} = \mu_{Placebo}$  versus  $H_1: \mu_{iNO\ 75} > \mu_{Placebo}$  for at least one realization.

**Table 32: Summary of 6MWD and Drug Adherence Analysis**

Variable	Model	Population	Factors
----------	-------	------------	---------

Variable	Model	Population	Factors
The Change from baseline in 6MWD for drug adherence at Week 18	ANCOVA	ITT	Treatment Group, Prostanoid Usage and Baseline

### 7.6.7 The Number of Subjects with Unsatisfactory Clinical Response from Baseline to 18 Weeks

The proportions of patient with unsatisfactory clinical response from baseline at Week 18 will be analyzed using Cochran Mantel Haenszel test (Table 33).

**Hypothesis:**

H0: PiNO 75 = PPlacebo versus H1: PiNO 75 < PPlacebo for at least one realization.

P: Proportions of patients with unsatisfactory clinical response.

SAS code:

SAS code as below:

```
PROC FREQ DATA = DATA;
```

```
TABLES TREAT*PROSSTATUS*RESP / CMH NOPERCENT NOCOL;
```

```
WEIGHT FREQ;
```

```
RUN;
```

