11.1.6. Borg Dyspnea Scale

The Borg Dyspnea Scale, Heart Rate and SpO₂ will be recorded in Part 1 at each study visit prior to, and immediately following, the 6MWT at Screening, Weeks 2, 6, 10, 14, and 18, including early discontinuation ([ATS Statement 2002](#)) and in Part 2, at week 16, week 32 and week 52. The BDS measures perceived breathlessness on a scale of 0 (none) to 10 (maximum) and has a minimally clinically important difference (MCID) of 1 point ([Table 4](#)) ([Ries 2005](#)).

Table 4: Borg Dyspnea Score

Score	Severity
0	Nothing at all
0.5	Very, very slight (just noticeable)
1	Very slight
2	Slight (light)
3	Moderate
4	Somewhat severe
5	Severe (heavy)
6	---
7	Very severe
8	---
9	---
10	Very, very severe (maximal)

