16. STATISTICAL CONSIDERATIONS

This section provides a general description of the statistical methods to be used in analyzing both safety and efficacy data. The key statistical issues or considerations will be addressed. A more detailed statistical analysis plan will be provided in a separate document that will be finalized before unblinding of treatment assignment.

Unless otherwise specified, all statistical tests will be one-sided with a significance level of 0.025. Summary statistics will be provided for all study variables with descriptive statistics (number of observations, mean, standard deviation, median, minimum, and maximum) for numerical (or continuous) variables and with frequency and percentage for categorical variables.

All statistical analysis will be conducted using SAS version 9.2 or higher (SAS Institute Inc., Cary, NC).

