16.3.3. Tertiary Endpoints

1. Change in health-related quality of life (using SF-36 version 2 health survey), with iNO as compared to placebo, from baseline to 18 weeks
2. Change in pulmonary hemodynamics (i.e., cardiac output [CO], cardiac index [CI], mean pulmonary artery pressure [mPAP], mean pulmonary capillary wedge pressure [mPCWP], systolic pulmonary artery pressure [sPAP], diastolic pulmonary artery pressure [dPAP], pulmonary vascular resistance [PVR], and oxygen saturation by pulse oximeter [SpO₂], mixed venous O₂, and right atrial pressure [RAP]) measured by right heart catheterization (RHC), with iNO as compared to placebo, from baseline to 18 weeks, in a subset of subjects (approximately 50), at selected sites
3. Change in echocardiogram measurements right ventricular function (including right ventricular fractional area change, systolic pulmonary artery pressure [sPAP], tricuspid annular motion/tricuspid annular plane systolic excursion, tricuspid annular systolic velocity, and Tei index) and left ventricular function (including left ventricular ejection fraction [LVEF], LV size, and improvement in LV early diastolic relaxation velocity), with iNO as compared to placebo, from baseline to 18 weeks, in a subset of subjects (approximately 50), at selected sites
4. Change in NT-proBNP, with iNO as compared to placebo, from Screening to 18 weeks
5. Change in Borg dyspnea score immediately following 6MWT, with iNO as compared to placebo, from baseline to 18 weeks
6. Change in 6MWD as related to degree of drug adherence, with iNO as compared to placebo, from baseline to 18 weeks
7. The number of subjects with unsatisfactory clinical response, with iNO as compared to placebo, from baseline to 18 weeks. Defined as: WHO Functional Class III or IV symptoms with no improvement in 6MWD
8. Number of subjects undergoing heart-lung or lung transplantation, number of subjects listed for transplantation, and deaths while awaiting transplantation, from baseline to 18 weeks
9. Medical resource utilization, with iNO as compared to placebo, from baseline from baseline to 18 weeks

For continuous (or numerical) response endpoints, the statistical analyses will be performed using the same method as that for the primary efficacy endpoint. Binary (or dichotomized) response endpoints will analyzed by CMH test stratified by the prostanoid usage status.

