### Hypothesis:

The hypothesis to be tested is as follows;

$H_0: S_1(t) = S_2(t)$  versus  $H_1: S_1(t) > S_2(t)$  for at least one realization.

Where,  $S_1(t)$ : Survival Function for iNO 75 mcg/kg IBW/hr ;  $S_2(t)$ : Survival Function for matching Placebo

The following SAS code will be used for analysis:

```
PROC LIFETEST Data = TTCW notable;
  TIME Days*Censor (0);
  STRATA PROSSTATUS/GROUP = TREAT;
RUN;
```

**Missing Data:** Please refer to Section 6.3 for missing data imputation. Missing values will be imputed using the LOCF.

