#### Hypothesis:

$H_0: \mu_{iNO\ 75} = \mu_{Placebo}$  versus  $H_1: \mu_{iNO\ 75} > \mu_{Placebo}$  for at least one realization.

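### The SAP's CMH code tests prostanoid use instead of treatment, and its Borg alternative points towards harm

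*SAP*

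**What the plan says.** **Binary tertiary endpoints.** Protocol 16.3.3 states that binary response endpoints "will analyzed by CMH test stratified by the prostanoid usage status". The SAP hypotheses in 7.6.7, 7.6.8 and 7.6.10 compare a proportion on iNO with the same proportion on placebo; in 7.6.7 the quantity is defined as "P: Proportions of patients with unsatisfactory clinical response". The SAS code printed under all three is identical: "TABLES TREAT*PROSSTATUS*RESP / CMH NOPERCENT NOCOL". For time to clinical worsening (SAP 7.4.1) the same two variables appear as "STRATA PROSSTATUS/GROUP = TREAT", with prostanoid status as the stratum and treatment as the compared group.

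**Borg dyspnea.** Protocol 11.1.6 and SAP Table 11 define a scale from 0 (no breathlessness) to 10 (maximal). SAP 7.6.5 analyses change from baseline at Week 18 by ANCOVA and writes the alternative as the iNO mean exceeding the placebo mean. It has no line stating which direction is favourable. On sidedness, Protocol 16 says: "Unless otherwise specified, all statistical tests will be one-sided with a significance level of 0.025".

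**The concern.** In PROC FREQ, a request `A*B*C / CMH` cross-tabulates B by C within levels of A. With `TREAT` first, treatment becomes the stratum, and the Mantel-Haenszel statistic measures whether prostanoid use is associated with response within arms. The CMH test is not symmetric in this respect: changing the stratum changes the null hypothesis. Run as written, the p-values reported for unsatisfactory response, transplantation and hospitalization would not be treatment comparisons. SAP section 11, which should list changes from the protocol, is empty, so this is not a declared departure.

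For Borg, benefit is a lower score, but the stated alternative is that iNO is higher. The sign is not uniform boilerplate, because the SAP varies it by endpoint: less-than for WHO functional class (7.4.2, also lower-is-better), greater-than for SF-36 (7.6.1, higher-is-better) and not-equal for NT-proBNP (7.6.4). A one-sided test in the written direction would reward worsening.

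**Working it through.** The plan gives no figure for these analyses, so there is none to reproduce. The check compares the two variable orders on constructed data and then works through the Borg direction.

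**Inputs.** 75 per arm is from SAP 5.4. The response rates (about 20% and 45%) and the near-even prostanoid split (38 and 37 per arm) are assumptions for illustration; the documents give neither.

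**Formula.** For each stratum with total n, row totals r1 and r2, and column totals c1 and c2: expected count E = r1·c1/n and variance V = r1·r2·c1·c2/[n²(n−1)]. Then chi-square = (Σ(observed − E))² / ΣV on 1 df.

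**Case A: treatment effect only.** Events: iNO 8/38 and 7/37; placebo 17/38 and 17/37 (the two prostanoid groups in order).

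| Order | Stratum | Observed − E | V |
|---|---|---|---|
| Intended (stratum = prostanoid) | group 1 | 8 − 12.5 = −4.5 | 4.250 |
| | group 2 | 7 − 12 = −5 | 4.110 |
| As coded (stratum = treatment) | iNO | 8 − 7.6 = 0.4 | 3.040 |
| | placebo | 17 − 17.227 = −0.227 | 4.709 |

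- Intended: (−9.5)²/8.360 = 10.80, p=0.001.
- As coded: (0.173)²/7.749 = 0.004, p=0.95.

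**Case B: prostanoid effect only, identical arms.** Events in each arm: 8/38 and 17/37.

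- As coded: in each arm 8 − 12.667 = −4.667 and V = 4.222, so (−9.333)²/8.444 = 10.32, p=0.001.
- Intended: observed equals expected in both strata, so chi-square is 0, p=1.0.

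**Simulation.** 20,000 trials per scenario, same rates, prostanoid share 30%, 50% and 70%, two-sided 0.05:

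| Truth | Rejection as coded | Rejection intended |
|---|---|---|
| Treatment effect only | about 5% | 91–92% |
| Prostanoid effect only | 85–92% | about 5% |

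**Borg.** Take a true 1-point benefit (the minimal important difference in Protocol 11.1.6), 75 per arm, one-sided 0.025 and a normal approximation. The SD is assumed. SE = SD·√(2/75). The probability of significance is Φ(−1/SE − 1.96) under the written alternative and Φ(1/SE − 1.96) under the reversed one.

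| Assumed SD | SE | Written (iNO > placebo) | Reversed (iNO < placebo) |
|---|---|---|---|
| 1.5 | 0.245 | <0.0001% | 98% |
| 2 | 0.327 | <0.0001% | 86% |
| 2.5 | 0.408 | 0.0005% | 69% |
| 3 | 0.490 | 0.003% | 53% |

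By symmetry, a true 1-point harm would be significant under the written alternative with the probabilities in the last column. Equivalently, a benefit with two-sided p=0.01 has p=0.01/2=0.005 in the correct direction and 1 − 0.005=0.995 in the written one.

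**The case against.** The governing text for the CMH analyses is right. The protocol names the stratum, the SAP hypotheses compare the arms, and Tables 33 and 34 list treatment and prostanoid usage as factors. Only template code is wrong, and an attentive programmer would probably notice. That is fair, but the SAP offers the code as what will be run. A pre-specified plan should not rely on someone spotting the conflict, least of all after unblinding.

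For Borg, SAP 7.6.5 states no sidedness, whereas SF-36 is explicitly one-sided. The mean-comparison code in 7.3.1 (least-squares means with differences and confidence limits) produces two-sided p-values. If that is what is reported, the estimate, interval and p-value would all be correct. This stands in part: the treatment difference and its confidence interval are unaffected in any case, and the harm is confined to a one-sided p-value in the written direction. But the protocol default is one-sided and the hypothesis is written with a direction, so that p-value is what the plan specifies.

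All the affected analyses are tertiary and carry no multiplicity adjustment (SAP 7.6). This stands and limits the importance. The worked rates, splits and SDs are illustrative; the mechanism does not depend on them.

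**Conclusion.** Both defects hold as written. The code in SAP 7.6.7, 7.6.8 and 7.6.10 tests prostanoid use against response. It has only about a 5% chance of flagging a real treatment effect when prostanoid use is unrelated to response, and under the assumed rates an 85–92% chance of a spurious result when only prostanoid use matters. The Borg alternative is reversed: with a true 1-point benefit and an SD between 1.5 and 3, a one-sided test as written reaches significance less than 0.004% of the time. The Borg consequence assumes that the protocol's one-sided default is applied. The primary 6MWD test, time to clinical worsening, WHO class, the gatekeeping order and the interim rules are untouched. This should be corrected, but it does not threaten the confirmatory result.

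**What to change.** Before unblinding:

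- In SAP 7.6.7, 7.6.8 and 7.6.10, change the request to `TABLES PROSSTATUS*TREAT*RESP / CMH`.
- In SAP 7.6.5, restate the alternative as iNO less than placebo, and add a line saying that smaller is better, as 7.4.2 does for WHO class.
- While editing, state how the one-sided p-value is obtained from the CMH chi-square, which is itself non-directional. The signed square root referred to the normal distribution would do.
- In 7.6.10, correct the definition of P, which still refers to transplantation although the endpoint is hospitalization.

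The essential change is about five lines: three code statements, one inequality and one direction line. Data collection, sample size and trial conduct do not change.

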**Table 33: Summary of Clinical Response Analysis**

Variable	Model	Population	Factors
Proportions of patients with unsatisfactory clinical response	CMH	ITT	Treatment Group and Prostanoid Usage

### 7.6.8 Subjects Undergoing Heart-Lung or Lung Transplantation, Number of Subjects Listed for Transplantation, and Deaths while Awaiting Transplantation, from Baseline to 18 Weeks

The proportions of patients undergoing heart-lung or lung transplantation, listed for transplantation and deaths while transplantation from baseline at Week 18 will be analyzed using Cochran Mantel Haenszel test (Table 34).

**Hypothesis:**

H0: PiNO 75 = PPlacebo versus H1: PiNO 75 < PPlacebo for at least one realization.

P: Proportions of patients undergoing heart-lung or lung transplantation from baseline to Week 18.

SAS code:

SAS code as below:

```

PROC FREQ DATA = DATA;
TABLES TREAT*PROSSTATUS*RESP / CMH NOPERCENT NOCOL;
WEIGHT FREQ;
RUN;

```

**Table 34: Summary of Analysis**

Variable	Model	Population	Factors
Proportions of patients undergoing heart or lung transplant	CMH	ITT	Treatment Group and Prostanoid Usage

### 7.6.9 Medical Resource Utilization from Baseline to 18 Weeks

The medical resource utilization will be summarized.

### 7.6.10 Hospitalization

The proportions of patients undergoing hospitalization will be analyzed using Cochran-Mantel-Haenszel test.

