11.1.24. Medical Resource Utilization

For the purpose of economic evaluation of the use of iNO as compared to placebo, medical healthcare resource utilization (HRU) will be recorded in Part 1.

At Screening, subjects will be asked about the number of hospitalizations, ER visits, and outpatient visits in the previous year. At each visit thereafter, the Investigator will record the subject's HRU in terms of number of hospitalizations and outpatient medical care, including ER visits, since the previous scheduled visit. The collection of HRU will continue through EOS.

A hospitalization is defined as any visit to the hospital requiring an overnight stay. The frequency and duration of any inpatient hospitalization will be recorded along with the primary reason for the hospitalization and the primary and secondary diagnosis at discharge. For each hospitalization, the duration spent in each of the following will be recorded: intensive care unit, general ward, emergency room, other, along with the type of physician consulted.

The frequency of unscheduled outpatient visits will be recorded along with the type of provider and type of facility visited, including the ER. An unscheduled outpatient visit is defined as any visit with a medical practitioner, in the office or at home, apart from the study visits.

Additionally, any procedures conducted during hospitalization or unscheduled outpatient visits will be recorded in the eCRF.

HRU forms should be reviewed by the Investigator for potential AEs. If AEs or SAEs are confirmed, then the Investigator must record the events as per instructions given in [Section 15.1](#) of the protocol.

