**IX. Number of Hospitalizations:**

The number of PAH specific hospitalizations (Table 16) will be summarized and analyzed between the treatment.

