**Table 16: Number of Hospitalizations**

Variables	Module	Source of Data	Variable specific derivation	Derivation	Comments(to be deleted later)
Hospitalization Status	Additional Inpatient Hospitalization (AIPH)	CRF	No, CRF data.	No.	

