#### Hypothesis:

$H_0: P_{iNO\ 75} = P_{Placebo}$  versus  $H_1: P_{iNO\ 75} < P_{Placebo}$  for at least one realization.

P: Proportions of patients undergoing heart-lung or lung transplantation from baseline to Week 18.

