#### SAS code:

SAS code as below:

```

PROC FREQ DATA = DATA;
TABLES TREAT*PROSSTATUS*RESP / CMH NOPERCENT NOCOL;
WEIGHT FREQ;
RUN;

```

Total duration of hospitalization will be summarized by treatment arm and analysed using appropriate statistical test as part of exploratory analysis.

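### The SAP's hospitalisation test does not measure the tertiary endpoint it is meant to serve, and its printed code does not compare the arms

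*SAP*

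**What the plan says.** **Endpoint.** SAP 4.3 IX: "The number of PAH specific hospitalizations (Table 16) will be summarized and analyzed between the treatment". The unit is admissions, and the cause is restricted to PAH.

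**Derivation.** SAP Table 16 takes hospitalisation status from a CRF module called Additional Inpatient Hospitalization (AIPH). Both derivation columns say that nothing is derived.

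**Test.** SAP 7.6.10: "The proportions of patients undergoing hospitalization will be analyzed using Cochran-Mantel-Haenszel test". The unit is now patients, and PAH is not mentioned.

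**Hypothesis.** In the same section the parameter is defined as "P: Proportions of patients undergoing heart-lung or lung transplantation from baseline to Week 18". SAP 7.6.8, on transplantation, has the identical line.

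**Code.** The statement printed in 7.6.10 is "TABLES TREAT*PROSSTATUS*RESP / CMH NOPERCENT NOCOL". RESP is not defined.

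**Other content of 7.6.10.** "Total duration of hospitalization will be summarized by treatment arm and analysed using appropriate statistical test as part of exploratory analysis".

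**Data collected.** Protocol 11.1.24 counts any overnight hospital stay as a hospitalisation and states: "The frequency and duration of any inpatient hospitalization will be recorded along with the primary reason for the hospitalization". Discharge diagnoses are recorded as well.

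**Elsewhere.** PAH hospitalisation is also a component of time to clinical worsening (TTCW). There it is adjudicated, sourced from the adjudication module (SAP Table 4) and tested separately by stratified log-rank (SAP Table 26).

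**The concern.** The endpoint section and the analysis section describe different variables. They differ in unit (admissions against patients) and in cause (PAH-specific against unrestricted). A programmer working from 4.3 IX and another working from 7.6.10 would produce different tables, and each could claim to have followed the SAP. The P line, read alone, names a third variable.

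Two things are at stake. First, if admissions unrelated to PAH enter the analysis at similar rates in both arms, they pull the comparison towards no difference. The report could then carry an unrestricted hospitalisation result beside the adjudicated TTCW component without explaining why the case definitions differ. Second, if the printed code is run as it stands, the p-value under the hospitalisation heading answers a question about prostanoid use.

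**Working it through.** The documents give no hospitalisation rate, power or sample size for this endpoint, so there is no plan figure to reproduce. The main check is a comparison of the text.

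**Step 1. The definitions side by side.**

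| Place in SAP | Unit | Cause | Source or test |
|---|---|---|---|
| 4.3 IX | Number of admissions | PAH-specific | Refers to Table 16 |
| Table 16 | Status; no counting rule | No filter given | AIPH module; no adjudication link |
| 7.6.10, text | Proportion of patients | None stated | CMH |
| 7.6.10, P line | Proportion of patients | Transplantation | Same line as 7.6.8 |
| Table 26 | Time to first event | PAH, adjudicated | Stratified log-rank |

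The first row has no matching analysis. Duration in 7.6.10 is neither a count nor restricted to PAH. Table 26 is PAH-specific but concerns time to a first event. Section 7.6.9 summarises medical resource utilisation with no stated PAH restriction.

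**Step 2. Repairing P alone is not enough.** Replacing transplantation with hospitalisation in the P line still leaves a proportion set against a count, and unrestricted cause set against PAH-specific.

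**Step 3. Count against proportion.** Take the planned 94 subjects per arm and suppose that 10 in each arm are hospitalised. Both proportions are 10/94 = 0.106. If one arm has 10 admissions and the other 25, the mean counts are 10/94 = 0.106 and 25/94 = 0.266 per subject. The proportion cannot show that difference.

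**Step 4. Effect of unrestricted cause (assumed rates, for illustration).** Let p be the PAH admission risk by Week 18 and q the non-PAH risk, with q the same in both arms and independent of p. The risk of any admission is 1 − (1 − p)(1 − q). Power uses the normal approximation for two proportions with n = 94 per arm and one-sided 0.025:

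power = Φ{[Δ − 1.96·√(2p̄(1 − p̄)/n)] / √([p₁(1 − p₁) + p₂(1 − p₂)]/n)}

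Here Δ is the risk difference and p̄ the mean of the two risks. For 10% against 5% with q = 0, this is Φ{[0.05 − 1.96 × 0.0384]/0.0382} = Φ(−0.66), or about 25%.

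| PAH risk, placebo vs iNO | q | Any admission | Risk ratio | Power |
|---|---|---|---|---|
| 10% vs 5% | 0% | 10.0% vs 5.0% | 0.50 | 25% |
| | 5% | 14.5% vs 9.75% | 0.67 | 17% |
| | 10% | 19.0% vs 14.5% | 0.76 | 13% |
| | 20% | 28.0% vs 24.0% | 0.86 | 9% |
| 20% vs 10% | 0% | 20.0% vs 10.0% | 0.50 | 48% |
| | 5% | 24.0% vs 14.5% | 0.60 | 38% |
| | 10% | 28.0% vs 19.0% | 0.68 | 31% |
| | 20% | 36.0% vs 28.0% | 0.78 | 22% |

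**Step 5. The printed code.** In a three-way TABLES request, PROC FREQ takes the first variable as the stratum and cross-tabulates the last two. With TREAT first, the statement tests prostanoid status against response within each arm. A constructed data set shows the consequence. Let 5 of 47 subjects respond in each prostanoid stratum of one arm and 14 of 47 in each stratum of the other, so that only treatment matters.

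- Stratified by prostanoid status: each stratum has 19 responders among 94, so 9.5 are expected in the first arm. The deviation is 2 × (5 − 9.5) = −9. The variance is 2 × (47 × 47 × 19 × 75)/(94² × 93) = 7.66. Chi-square = 81/7.66 = 10.57, p = 0.001.
- In the printed order: response is the same in both prostanoid groups within each arm, so the deviation is 0. Chi-square = 0.00, p = 1.00.

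A clear treatment difference disappears completely.

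**The case against.** Several points on the other side have force.

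- **The P line.** A reader might infer that the SAP plans to test transplantation under this heading, so that a PAH admission without transplant would be a non-event. The documents do not support that. The heading and the operative sentence both say hospitalisation, and the line matches 7.6.8 word for word. It is a copying error.
- **Any cause.** A reader might infer that the SAP states an all-cause test. It does not: 7.6.10 is silent on cause and could be meant to inherit the PAH restriction from 4.3 IX. With no filter in Table 16 and an all-cause definition in the protocol, unrestricted is the plain reading, but it is still an inference.
- **Table 16.** A reader might take its entries as a decision against filtering. They look like template text. Table 10 labels NT-proBNP as CRF data although it gives the source as non-CRF, and Table 9 shows no derivation for PVR although Protocol 11.1.13.2 has a formula. Nor do the documents show what AIPH contains or tie it to the protocol's resource-utilisation recording. What stands is that a rule is absent, not that one was ruled out.
- **Coverage elsewhere.** Adjudicated PAH hospitalisation is compared between arms in Table 26, so it would be wrong to say that it goes unanalysed. If that result differed from an unrestricted proportion, this would be no contradiction, because the variables differ. Even so, the count named in 4.3 IX is analysed nowhere.
- **Importance.** Hospitalisation is not a separate item among the protocol's tertiary endpoints, and the SAP makes no multiplicity adjustment at this tier. This is correct and limits the weight of the point.

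**Conclusion.** The point holds as a mismatch between stated endpoint and stated analysis. SAP 4.3 IX calls for a count of PAH-specific hospitalisations. Table 16 does not say how to obtain it, and 7.6.10 tests a proportion with no stated restriction on cause. The code printed for that test does not compare the arms. The text and the code establish this without any assumption about rates.

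Its importance is low, for the reasons conceded above, and nothing in the primary, secondary or interim decisions uses the endpoint. The dilution figures rest wholly on assumed rates and on non-PAH admissions being equal in both arms. They show direction, not an expected loss. Even with perfect filtering, the assumed scenarios give power below 50%, so a reader should not conclude that the mismatch costs the trial a well-powered comparison.

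**What to change.** Make SAP 4.3 IX, Table 16 and 7.6.10 state one variable, before unblinding.

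1. In Table 16, source PAH hospitalisation from the adjudication module already used in Table 4.
2. In 7.6.10, define P as the proportion of subjects with at least one adjudicated PAH hospitalisation through Week 18, and reword 4.3 IX to match. Summarise the number of such admissions by arm with time on study as the denominator. If the count is to remain the tested endpoint, replace CMH with a count model that has a time-on-study offset.
3. If CMH is kept, write `TABLES PROSSTATUS*TREAT*RESP` and define RESP. SAP 7.6.7 and 7.6.8 print the same statement with TREAT first and need the same correction.
4. Report all-cause hospitalisation under medical resource utilisation (7.6.9).

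The cost is SAP wording and programming. The plan already provides for adjudication of PAH hospitalisation and for recording the reason for admission, so no new data collection is needed. The proportion in item 2 will overlap with the log-rank component in Table 26. The SAP should say that both use the same adjudicated events.
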